3. STUDY DESIGN

3.1. Study Description and Duration

This prospective, open-label, single-center, non-randomized, investigator-sponsored clinical study seeks to investigate the benefit of managing patients with DED with a sustained release intracanalicular dexamethasone (0.4 mg) insert in addition to Restasis compared to Restasis in conjunction with Lotemax and Restasis alone. In addition, this study will evaluate the ease of DEXTENZA® insertion.

After screening a given patient for inclusion and exclusion criteria, and gaining informed consent, both eyes will be prescribed Restasis. Both eyes of 10 patients will be selected to receive DEXTENZA® insertion (study group), while 10 patients will be prescribed Lotemax and 10 patients will be on Restasis monotherapy (control groups). Per patient, the study period will last for approximately 12 weeks after the DEXTENZA® insertion, consisting of one screening/prescription visit and 5 post-procedure follow-up visits (week 1, week 2, week 4, week 8 and week 12). At week 1, week 2, week 4, week 8 and week 12, primary and secondary endpoints will be assessed alongside standard-of-care procedures. Adjusting for enrollment period, the study will last a total of approximately 9 months.

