1. INTRODUCTION AND RATIONALE

1.1. Introduction

Dry eye disease (DED) is a multifactorial disorder of the ocular surface that severely impacts vision and quality of life. Risk factors that contribute to DED include age, gender, hormones, autoimmune disorders, local environment, use of video displays, contact lens wear and exposure to medications/preservatives, all potentially leading to secretory or evaporative DED, or both.¹ The Tear Film and Ocular Surface Society's Dry Eye Workshop II definition recognizes the impact of inflammation, saying, "Dry eye is a multifactorial disease of the ocular surface characterized by a loss of homeostasis of the tear film, and accompanied by ocular symptoms, in which tear film instability and hyperosmolarity, ocular surface inflammation and damage, and neurosensory abnormalities play etiological roles."²

Topical cyclosporine A (Restasis) is indicated to increase tear production in patients whose tear production is presumed to be suppressed because of ocular inflammation associated with DES. A significant number of studies are available concerning the use of cyclosporine as a way to modulate inflammation. Positive effects are consistently seen with the use of this drug for treatment of DES.³ Topical application exerts a therapeutic effect without causing systemic side effects, because only small amounts can penetrate into the bloodstream after topical application.⁴

After determining the severity of the inflammation in a DED patient, the doctor can then decide if a topical steroid is needed to quickly decrease the overall inflammation along with Restasis.

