1.2.1. Rationale for Study Design

This prospective study will use a head to head design for 30 participants, 60 eyes. All eyes will receive bilateral Restasis. The study group will consist of 20 eyes receiving DEXTENZA® insertion. The control groups will consist of 20 eyes receiving Lotemax and 20 eyes will have Restasis monotherapy.

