4.1.1. Inclusion Criteria

A patient's study eye must meet the following criteria to be eligible for inclusion in the study:

- 18 years of age or older
- Signs and symptoms of DED
- Consent to treat with topical immunomodulator
- Willing and able to comply with clinic visits and study related procedures
- Willing and able to sign the informed consent form

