5.1.1. Study Procedures

Screening/Prescription

After the patient has provided informed consent, the following information will be collected:

- Inclusion/exclusion
- Demographics
- Medical history and concurrent illnesses
- Concomitant medications
- UCVA and MR/BCVA as measured by ETDRS chart at 4m
- Ophthalmic Examination with dilation
- Intraocular pressure
- Meibomian gland assessment (expressibility and quality)
- DED Assessment
 - Schirmer's
 - MMP9
 - Osmolarity
 - Conjunctival injection
 - TBUT
 - Ocular surface staining (sodium fluorescein and lissamine green)
- Subject reported AE's
- Restasis BID OU prescription
- Lotemax BID OU for 1 month prescription
- DEXTENZA® insertion in one eye

- Insert Visualization
- Physician ease of insertion questionnaire
- DEQ-5 

Week 1, Week 2, Week 4 and Week 8

- UCVA and MR/BCVA as measured by ETDRS chart at 4m
- Concomitant Medications
- Ophthalmic Examination without dilation and with IOP
- Insert visualization
- Meibomian gland assessment (expressibility and quality)
- DED Assessment
 - Schirmer's
 - MMP9
 - Osmolarity
 - Conjunctival injection
 - TBUT
 - Ocular surface staining (sodium fluorescein and lissamine green)
- Subject reported AE's
- DEQ-5 

Week 12

- UCVA and MR/BCVA as measured by ETDRS chart at 4m
- Concomitant Medications
- Ophthalmic Examination without dilation and with IOP
- Insert visualization
- Meibomian gland assessment (expressibility and quality)
- DED Assessment
 - Schirmer's
 - MMP9
 - Osmolarity
 - Conjunctival injection
 - TBUT
 - Ocular surface staining (sodium fluorescein and lissamine green)
- Subject reported AE's
- DEQ-5 

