I. The investigator will use the NEI scale to grade the cornea using fluorescein and the conjunctiva using lissamine green at visits 1, 2, 3, 4, 5, 6.

II. The investigator will grade the level of ocular injection on a 0 to 4-point scale at visits 1, 2, 3, 4, 5, 6.

0 = None

1 = Mild – Slightly dilated blood vessels; color of vessels is typically pink; can be quadrantal

2 = Moderate – More apparent dilation of blood vessels; vessel color is more intense (redder); involves the majority of the vessel bed

3 = Severe – Numerous and obvious dilated blood vessels; in the absence of chemosis the color is deep red, may be less red or pink in presence of chemosis, is not quadrantic

4 = Extremely Severe – Large, numerous, dilated blood vessels characterized by unusually severe deep red color, regardless of grade of chemosis, which involves the entire vessel bed

III. The investigator will evaluate the expressibility and quality of the meibomian glands at visits 1, 2, 3, 4, 5, 6..

Grade scale for meibomian gland dysfunction		
Grade Scale	Percentage of blocked glands	Quality of meibomian secretion
Grade 1	40% - 50%	Clear to mild milky secretion
Grade 2	50% - 70%	Milky to pasty secretion
Grade 3	70% - 85%	Thick, pasty to very little secretion
Grade 4	85% - 90%	Very little to no secretion

IV. The investigator will use the InflammaDry to detect levels of MMP9 at visits 1, 2, 3, 4, 5, 6.

[figure not shown]

InflammaDry

[name] STUDY V1

V. The investigator will use Tear Lab to assess tear osmolarity at visits 1,2, 3, 4, 5, 6.

VI. The investigator will fill out the following questionnaire on the day of DEXTENZA® insertion (Screening visit):

Physician Ease of Insertion Questionnaire

The investigator will grade the level of ease of insertion of the intracanalicular insert on a 0 to 10-point scale.

The Investigator will record ease of insertion procedure on the appropriate Case Report Form.

0	1	2	3	4	5	6	7	8	9	10
---	---	---	---	---	---	---	---	---	---	----

Very Easy

Very Hard

VII. The investigator will have the patient complete the DEQ-5 questionnaire at visits 1,3,4,5,6,7.

DEQ-5

1. Questions about EYES DRYNESS:

a. During a typical day in the past month, how often did your eyes feel discomfort?

Never
 Rarely
 Sometimes
 Frequently
 Constantly

b. When your eyes feel discomfort, how intense was this feeling of discomfort at the end of the day, within two hours of going to bed?

Never have it Not at all intense Very intense

0
 1
 2
 3
 4
 5

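### The between-arm hypotheses rest on an allocation that the protocol calls non-randomised and the SAP calls randomised, with no method in either, so the contrast is open to selection bias

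*Protocol*

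**What the plan says.** - **Design.** Protocol section 3.1 opens: "This prospective, open-label, single-center, non-randomized, investigator-sponsored clinical study". It fills the arms as follows: "Both eyes of 10 patients will be selected to receive DEXTENZA® insertion (study group), while 10 patients will be prescribed Lotemax", with a further 10 on Restasis alone. It does not say who selects, on what basis or in what order.
- **Comparative aim.** Protocol section 1.2.1: "This prospective study will use a head to head design for 30 participants, 60 eyes". Section 1.2 adds two between-arm hypotheses: greater symptomatic improvement than pharmacotherapy alone, and non-inferiority to Restasis with Lotemax.
- **Timing.** Table 1 puts screening, assessments, prescriptions and insertion at Visit 1. Section 5.1.1 lists the dry-eye signs, including the staining that forms the primary endpoint, ahead of items such as "Lotemax BID OU for 1 month prescription" and the insertion. DEQ-5 comes last in that list.
- **Entry and grading.** The only disease criterion for entry is "Signs and symptoms of DED", with no minimum score. Appendix I: "The investigator will use the NEI scale to grade the cornea using fluorescein and the conjunctiva using lissamine green". No masked grader is described.
- **SAP.** The Patients section and the Discussion both say the patients were randomised. Neither gives a sequence, blocking or concealment. The Statistical Analysis section describes repeated measures ANOVA within each group and Bonferroni comparisons with baseline. It describes no between-group test and no baseline adjustment.

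**The concern.** A head-to-head contrast can be read as a drug effect only if assignment is independent of prognosis. Here the protocol's own wording allows the arm to be chosen when the baseline signs may already be known, in an open-label study with wide entry criteria.

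If patients with high baseline scores are steered to one arm, that arm regresses further towards the mean and shows extra improvement without any drug effect. If patients who seem easier to treat or more adherent are steered to the insert, the bias comes from traits that were never measured. Both hypotheses in section 1.2 are exposed.

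The SAP tests only within groups, but it still compares groups in words. The Discussion says the two steroid groups gave similar results, and the Conclusion presents the insert as a safe alternative to topical steroids.

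**Working it through.** **1. What can be reproduced.** The documents give no power, effect size, planning SD or non-inferiority margin, so there is no sample-size figure to rebuild. The counts add up: 10 + 10 + 10 = 30 patients and 60 eyes planned; 10 + 11 + 9 = 30 patients and 20 + 22 + 18 = 60 eyes reported.

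**2. Do the group sizes reveal the method?** Under simple 1:1:1 randomisation the probability of sizes 10, 11 and 9 in any order is 6 × 30!/(10! 11! 9!)/3^30 = 6 × 0.0245 = 0.147. That is unremarkable, so the sizes do not settle how patients were assigned.

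**3. Do the printed baselines show selection?** DEQ-5 means (SAP Results) are 14.1 (SD 4.0), 14.4 (2.4) and 14.4 (3.7). The pooled SD is sqrt((9 × 4.0² + 10 × 2.4² + 8 × 3.7²)/27) = 3.39, so the largest gap is 0.3/3.39 = 0.09 SD. For signs (SAP Table 2), SMD is the difference in means over sqrt((SD1² + SD2²)/2). The p value is from a three-group ANOVA at patient level (10/11/9), using the printed SDs.

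| Sign | Insert | Loteprednol | Monotherapy | SMD, insert v loteprednol | p |
|---|---|---|---|---|---|
| Corneal staining | 0.6 | 0.8 | 0.5 | -0.16 | 0.83 |
| Conjunctival staining | 0.5 | 1.5 | 0.4 | -0.56 | 0.22 |
| Schirmer (mm) | 14.9 | 10.3 | 11.6 | 0.52 | 0.52 |
| TBUT (s) | 6.6 | 5.4 | 5.7 | 0.64 | 0.50 |
| Osmolarity | 295.5 | 311.3 | 306.9 | -0.85 | 0.26 |
| Meibomian score | 8.7 | 7.1 | 9.2 | 0.71 | 0.13 |

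(The Results text gives 0.5, not 0.6, for corneal staining in the insert group.) Counting eyes as independent lowers two p values, to 0.047 (conjunctival staining) and 0.016 (meibomian score). But both eyes of a patient share an arm, and over six signs the smaller becomes 6 × 0.016 = 0.096. The gaps are compatible with chance.

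**4. How large could the effect be?** This is an illustration with assumed inputs.
- There are 30 patients and no drug effect. Baseline and follow-up share a true score with reliability r, each with independent error.
- Patients are ranked on rho × baseline + sqrt(1 - rho²) × noise. A steroid arm is every second patient of the top 20, and monotherapy is the bottom 10.
- The expected spurious difference in change is -(1 - r) × baseline gap. The gap comes out at 0.50 SD for rho 0.3 and 1.00 SD for rho 0.6.

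For r = 0.7 and rho = 0.6 this gives -(0.3 × 1.00) = -0.30 SD, or 0.30 × 3.39 = 1.0 DEQ-5 point. From 40,000 simulated trials per setting, two-sided 5% level:

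| r | rho | Bias (SD) | DEQ-5 points | t test on change rejects | Baseline-adjusted test rejects |
|---|---|---|---|---|---|
| 0.5 | 0.3 | -0.25 | 0.8 | 8% | 5% |
| 0.5 | 0.6 | -0.50 | 1.7 | 19% | 5% |
| 0.7 | 0.3 | -0.15 | 0.5 | 7% | 5% |
| 0.7 | 0.6 | -0.30 | 1.0 | 13% | 5% |
| 0.8 | 0.3 | -0.10 | 0.3 | 6% | 5% |
| 0.8 | 0.6 | -0.20 | 0.7 | 10% | 5% |

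At rho = 0 the t test rejects 5%.

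**The case against.** The strongest objection is that the SAP says the patients were randomised. If so, selection did not occur. That has force, and it is why the point concerns an unspecified and contradictory allocation rather than a demonstrated bias. It does not close the matter, because the SAP names no procedure and the protocol contains none.

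A reader might infer that the investigator chose each arm by severity, because section 1.1 says: "After determining the severity of the inflammation in a DED patient, the doctor can then decide if a topical steroid is needed". That sentence is general background on practice, not an allocation rule. The order of items in section 5.1.1 suggests a sequence of procedures but does not fix one. The printed data do not show that pattern either. The insert group has the best baseline osmolarity, Schirmer score and TBUT of the three, which is not what steering the worst patients to steroids would produce. The loteprednol group looks worse than the insert group on five signs, but those signs may be correlated and the groups are small.

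The illustration also has limits, and these objections stand:
- The t test on change is not in the SAP, which tests only within groups.
- Arm choice in the model depends on the measured score plus noise, so the whole modelled inflation disappears with baseline adjustment.
- DEQ-5 supplies the scale, but it is a secondary outcome listed after treatment at Visit 1.
- The normal model does not carry over to corneal staining, where 50% to 70% of eyes scored zero at baseline.

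**Conclusion.** The point holds as a design weakness. The protocol sets superiority and non-inferiority hypotheses between arms, plans a non-randomised, open-label allocation by selection, and gives no sequence, concealment or rule. The SAP contradicts it without describing a method. The between-arm contrast is therefore open to selection bias.

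It does not follow that selection took place, or that the reported results are biased; the documents establish neither.

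The size rests on assumed reliability of 0.5 to 0.8 and rho of 0.3 to 0.6. Over that range an unadjusted comparison of change would reject about 6% to 19% of the time instead of 5%, and adjustment for the measured baseline removes the excess. The case for randomising rather than only adjusting rests on unmeasured traits such as expected adherence or ease of insertion. That part cannot be sized from the documents and cannot be adjusted away.

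**What to change.** **Protocol, for any patient not yet assigned.** In section 3.1, replace the non-randomised wording and the selection wording with 1:1:1 assignment by patient from a computer-generated, concealed list. Someone who neither enrols nor grades should hold it. Keep block sizes out of the protocol text, since an open-label single-site team could use them to guess the next arm. In section 5.1.1, add a step that opens the assignment only after eligibility, consent, DEQ-5 and all baseline grading are recorded, and before any prescription or insertion.

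**SAP, for patients already assigned.** The SAP reports results for all 30 patients, so this is the part that can be used now.
- Reconcile protocol section 3.1 with the SAP's Patients section and Discussion, and state who assigned patients and how.
- If it was by selection, remove the word randomised from the SAP. Report a patient-level, baseline-adjusted between-arm estimate with its confidence interval, and present every between-arm statement as descriptive and non-randomised, including the Discussion's remark on similar results.

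**Cost.** Prospectively: a protocol amendment, a matching change to the consent form and one list, with no extra patients, visits or procedures. The investigator gives up choice of arm, and a patient unwilling to accept any of the three arms cannot enrol. Retrospectively: text and one further analysis of data already collected.

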4. SELECTION, WITHDRAWAL, AND REPLACEMENT OF PATIENTS

4.1. Study Population

The study aims to enroll 60 eyes of 30 patients who exhibit signs and symptoms of DED, who have not been on topical immunomodulation for a minimum of 3 months, and who would benefit from addition of topical pharmacotherapy (immunomodulation).

4.1.1. Inclusion Criteria

A patient's study eye must meet the following criteria to be eligible for inclusion in the study:

- 18 years of age or older
- Signs and symptoms of DED
- Consent to treat with topical immunomodulator
- Willing and able to comply with clinic visits and study related procedures
- Willing and able to sign the informed consent form

4.1.2. Exclusion Criteria

A patient who meets any of the following criteria will be excluded from the study:

- Patients under the age of 18.
- Pregnancy (must be ruled out in women of child-bearing age with pregnancy test)

- Active infectious systemic disease
- Active infectious ocular or extraocular disease
- Altered nasolacrimal flow of either acquired, induced, or congenital origin
- Hypersensitivity to dexamethasone
- Patients who have been on topical immunomodulating agents in the previous 3 months to their baseline visit
- Patient being treated with either topical, oral, or intravenous immunosuppressive agents, immunomodulating agents, or steroid (including NSAIDS)
- Patients with severe disease that warrants critical attention, deemed unsafe for the study by the investigator

4.2. Treatment Logistics and Accountability

4.2.1. Packaging, Labeling, and Storage

Intracanalicular dexamethasone insert must be stored in a secure area accessible only to the Investigator and their designee(s) and refrigerated and stored between 2° C and 8° C. Intracanalicular dexamethasone insert contains 0.4 mg dexamethasone and is designed to provide a sustained and tapered release of therapeutic levels of dexamethasone to the ocular surface for up to 30 days for the reduction of post-surgical inflammation and pain associated with ocular surgery. Dexamethasone is an anti-inflammatory 9-fluoro-glucocorticoid (also termed a glucocorticoid agonist) and is the active

ingredient found in MAXIDEX® 0.1% (dexamethasone ophthalmic suspension), which contains approximately 50 µg of dexamethasone per drop.

Study inserts will be supplied by Ocular Therapeutix in a sealed foil pouch containing one intracanalicular dexamethasone insert in a foam carrier.

Study inserts will be shipped to the site via overnight shipping using cold packs to maintain a temperature of 2° to 8° C. The Investigator, or an approved representative (e.g. pharmacist), will ensure that all study drug inserts are stored in a secured area, under recommended storage conditions and in accordance with applicable regulatory requirements. The shipping box is to be opened and stored immediately at the site in a refrigerator intended for investigational products at a temperature of 2° to 8°C.

When the insert is removed from the refrigerator, it should be visually inspected. Exposure of the insert to temperatures outside these limits is not recommended. Records of actual storage conditions (i.e. temperature log) at the study site must be maintained; and must include a record of the dates, when the refrigerator was checked, the initials of person checking, and the temperature.

4.2.2. Supply and Disposition of Treatments

Study insert will be shipped at a temperature of 2° to 8°C to the investigator as needed during the study.

4.2.3. Treatment Accountability

All study insert accountability records will be kept current.

The investigator will account for all opened and unopened packaging of study inserts. These records will contain the dates, quantity, and study medication

- Inserted in each patient,
- disposed of at the site or returned to Ocular Therapeutix

All accountability records will be made available for inspection by regulatory agency inspectors.

4.3. Concomitant Medications and Procedures

At the discretion of their physician, patients may continue to receive all medications and standard treatments administered for other conditions.

5. STUDY SCHEDULE OF EVENTS AND VISIT DESCRIPTIONS

5.1. Schedule of Events

Study assessments and procedures are presented by visit in [Table 1](#).

[name] STUDY V2

Table 1 Schedule of Events

Study Procedure	Screening/ Prescription	Week 1	Week 2	Week 4	Week 8	Week 12
Visit	VISIT 1	VISIT 2	VISIT 3	VISIT 4	VISIT 5	VISIT 6
Windows for Visits	(Day -30 to -1)	+/- 1 day	+/- 3 days	+/- 3 days	+/- 3 days	+/- 3 days
vInclusion/Exclusion	x					
Informed Consent	x					
Demographics	x					
Medical History and Concurrent Illnesses	x					
Concomitant Medications	x	x	x	x	x	x
UCVA Testing	x	x	x	x	x	x
MR/BCVA (ETDRS at 4m)	x	x	x	x	x	x
Schirmer's Test	x	x	x	x	x	x
Ophthalmic Examination (w/ or w/o dilation)	x	x	x	x	x	x
Meibomian gland assessment (expressibility and quality)	x	x	x	x	x	x
MMP9 with Inflamma Dry	x	x	x	x	x	x
Tear Osmolarity with Tear Lab	x	x	x	x	x	x
Conjunctival Injection Scale 0-4	x	x	x	x	x	x
NaFl Staining	x	x	x	x	x	x
TBUT	x	x	x	x	x	x
Lissamine Green	x	x	x	x	x	x

[name] STUDY V2

Intraocular Pressure	x	x	x	x	x	x
Restasis/Lotemax prescription	x					
Intracanalicular dexamethasone insert	x					
Physician ease of insertion questionnaire	x					
Insert Visualization	x	x	x	x	x	x
Subject reported AEs after insertion	x	x	x	x	x	x
DEQ-5	x	x	x	x	x	x

Study Visit Descriptions

5.1.1. Study Procedures

Screening/Prescription

After the patient has provided informed consent, the following information will be collected:

- Inclusion/exclusion
- Demographics
- Medical history and concurrent illnesses
- Concomitant medications
- UCVA and MR/BCVA as measured by ETDRS chart at 4m
- Ophthalmic Examination with dilation
- Intraocular pressure
- Meibomian gland assessment (expressibility and quality)
- DED Assessment
 - Schirmer's
 - MMP9
 - Osmolarity
 - Conjunctival injection
 - TBUT
 - Ocular surface staining (sodium fluorescein and lissamine green)
- Subject reported AE's
- Restasis BID OU prescription
- Lotemax BID OU for 1 month prescription
- DEXTENZA® insertion in one eye

- Insert Visualization
- Physician ease of insertion questionnaire
- DEQ-5 

Week 1, Week 2, Week 4 and Week 8

- UCVA and MR/BCVA as measured by ETDRS chart at 4m
- Concomitant Medications
- Ophthalmic Examination without dilation and with IOP
- Insert visualization
- Meibomian gland assessment (expressibility and quality)
- DED Assessment
 - Schirmer's
 - MMP9
 - Osmolarity
 - Conjunctival injection
 - TBUT
 - Ocular surface staining (sodium fluorescein and lissamine green)
- Subject reported AE's
- DEQ-5 

Week 12

- UCVA and MR/BCVA as measured by ETDRS chart at 4m
- Concomitant Medications
- Ophthalmic Examination without dilation and with IOP
- Insert visualization
- Meibomian gland assessment (expressibility and quality)
- DED Assessment
 - Schirmer's
 - MMP9
 - Osmolarity
 - Conjunctival injection
 - TBUT
 - Ocular surface staining (sodium fluorescein and lissamine green)
- Subject reported AE's
- DEQ-5 

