Intracanalicular Dexamethasone used in conjunction with Restasis (cyclosporine ophthalmic emulsion) for the treatment of signs and symptoms of dry eye disease as compared to Restasis with Lotemax (loteprednol etabonate ophthalmic suspension 0.5%) and Restasis monotherapy.

[name] STUDY

Compound:

DEXTENZA® (dexamethasone ophthalmic insert) 0.4 mg for intracanalicular use

Study Name:

[name] STUDY

Protocol Number:

TC-2020-DexRes

Clinical Phase:

Open label prospective

Date of Issue:

01/11/2021

Primary Investigator:

[name]

Site Name & Location:

Cleveland Eye Clinic
[name],
[name]

[name] STUDY V2

CLINICAL STUDY PROTOCOL SYNOPSIS

TITLE	Intracanalicular Dexamethasone used in conjunction with Restasis (cyclosporine ophthalmic emulsion) for the treatment of signs and symptoms of dry eye disease as compared to Restasis with Lotemax (loteprednol etabonate ophthalmic suspension 0.5%) and Restasis monotherapy.
SITE LOCATION(S)	Cleveland Eye Clinic [name]
PRINCIPAL INVESTIGATOR	[name]
OBJECTIVE(S)	To evaluate the benefit of treatment with a physician administered intracanalicular dexamethasone insert in patients with dry eye who are beginning treatment with Restasis (cyclosporine ophthalmic emulsion) to reduce the signs and symptoms of dry eye disease.
STUDY DESIGN	Prospective Open-label Interventional Study
STUDY DURATION	6 months including screening and enrollment
ESTIMATED STUDY COMPLETION DATE	3 months after date of insertion
POPULATION	
Sample Size:	30 patients (60 eyes)
Target Population:	Patients with dry eye who are about to begin treatment with Restasis bilaterally to reduce the signs and symptoms of dry eye disease and who have not been on topical immunomodulation for a minimum of 3 months prior to the start of the study.
TREATMENT(S)	

[name] STUDY V2

Study Drug	Sustained Release Dexamethasone, 0.4 mg
Dose/Route/Schedule:	All patients will be prescribed Restasis BID for both eyes who have not been on topical immunomodulation for a minimum of 3 months, and who would benefit from addition of topical pharmacotherapy (immunomodulation). There will be 3 groups. 10 patients will receive Restasis BID and Dextenza in both eyes, 10 patients will receive Restasis BID for 12 weeks and Lotemax BID for one month in both eyes and 10 patients will receive Restasis BID monotherapy.

Screening/ Prescription

- 1-week
- 2-week
- 1 month
- 2 month
- 3 month

ENDPOINT(s)

PRIMARY:

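### The Visit 1 procedure list places the insert in one eye and does not separate treatments by group, while the synopsis, sections 1.2, 1.2.1 and 3.1 and the SAP have it in both eyes of 10 patients (10 versus 20 treated eyes)

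*Protocol*

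**What the plan says.** On how many eyes receive the insert, the documents read as follows.

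- Protocol, section 5.1.1, Screening/Prescription list: "DEXTENZA® insertion in one eye".
- Protocol synopsis, Dose/Route/Schedule: "10 patients will receive Restasis BID and Dextenza in both eyes".
- Protocol, section 1.2: the insert is described as bilateral.
- Protocol, section 1.2.1: "The study group will consist of 20 eyes receiving DEXTENZA® insertion".
- Protocol, section 3.1: both eyes of ten patients form the study group.
- Protocol, Table 1: one row for the insert at Visit 1, with no laterality.
- SAP, Patients: the study group had the insert placed in both eyes.
- SAP, Results: the insert group is 20 eyes of 10 subjects.

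On which group receives what, the synopsis and sections 1.2.1 and 3.1 put all patients on Restasis, add the insert in one group of ten, add Lotemax in a second group of ten, and leave the third on Restasis alone. The 5.1.1 list gives Restasis, then "Lotemax BID OU for 1 month prescription", then the insert, with no group named on any line. Table 1 has a single "Restasis/Lotemax prescription" row and a single insert row, also with no group named.

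**The concern.** Section 5.1.1 is what site staff work through at Visit 1, and it is the only visit-level text that says how many eyes receive the insert. The two lines directly above the insert line specify both eyes for the drops, so the change to one eye is hard to read as shorthand. An operative instruction that disagrees with the design can change what is actually given.

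Two things are at stake. The first is exposure. The SAP analyses 20 eyes as insert eyes, and if staff followed 5.1.1 some of those eyes would have had no insert. The second is clarity of assignment. A pooled list with no group labels leaves staff to look elsewhere for who receives the insert and who receives Lotemax, and that difference is the comparison the study exists to make.

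**Working it through.** **Inputs.** Ten patients per group and three groups (synopsis). Twenty planned insert eyes and 60 eyes in all (section 1.2.1). One insert eye per patient (section 5.1.1). Twenty analysed insert eyes of 10 subjects, 14 of them (70%) without corneal staining at baseline (SAP, Results). The documents contain no sample-size calculation, so the check is a direct count.

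**Step 1. The plan's own figure.** Insert eyes = patients in group × treated eyes per patient.
- Both eyes: 10 × 2 = 20, which matches section 1.2.1.
- All groups: 3 × 10 × 2 = 60, which matches the stated total.

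**Step 2. Section 5.1.1 as written.**
- One eye: 10 × 1 = 10, which does not match 20.
- Eyes receiving their group's full planned regimen: 10 + 20 + 20 = 50. The 60 enrolled eyes would be unchanged, because every patient still contributes two; only the treated count moves.

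**Step 3. Is the SAP denominator open?**
- Groups: 20 + 22 + 18 = 60 eyes, and 10 + 11 + 9 = 30 subjects.
- 14/20 = 70.0%, as reported. Neighbouring denominators do not fit: 14/19 = 73.7% and 14/21 = 66.7%. Fourteen eyes cannot come from a group of 10.
- The SAP therefore analysed 20 eyes in the insert group. This counts eyes analysed; it is not a count of inserts placed.

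**Step 4. Consequence if some analysed eyes had no insert.** Let Δ be the true per-eye effect of adding the insert, and k the number of patients (out of 10) treated in one eye only. Assume that an untreated fellow eye has no insert effect. The average effect over the 20 analysed eyes is Δ × (1 − k/20).

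| k | Untreated share | Average effect |
|---|---|---|
| 0 | 0/20 = 0% | 1.00 Δ |
| 5 | 5/20 = 25% | 0.75 Δ |
| 10 | 10/20 = 50% | 0.50 Δ |

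The values of k are scenarios. The SAP's account of insertion in both eyes corresponds to k = 0.

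**Step 5. The list without group labels.** Applied literally to all 30 patients, 5.1.1 would give 30 × 1 = 30 insert eyes and 30 × 2 = 60 Lotemax eyes, against 20 and 20 planned, and no monotherapy group. That cannot be squared with the synopsis or sections 1.2.1 and 3.1, so what the list shows is missing group labels, not a different assignment.

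**The case against.** The strongest reply is that this is one stray line. Four places in the protocol and the SAP agree with each other, and the SAP states in the past tense that both eyes received the insert. The study is single-center and investigator-sponsored, and its results are already written up, so rewording Visit 1 cannot change what was given. Section 4.2.3 already requires a record of the quantity of inserts used in each patient.

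Much of that stands. The weight of the text is on one side, and the dilution in Step 4 is a possibility that the SAP's account speaks against. But the conflict sits in the working instruction, and neither document gives a count of insertions performed. The accountability records are the means of settling the question; neither document reports that they were used for it.

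Other inferences go further than the documents allow.

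- **That the analysis denominator could be 10 or 20.** Section 1.2.1 and the SAP Results both give 20, and the 70% figure fits only 20.
- **That every patient is assigned Lotemax.** No text says so. The list is pooled, the insert is equally unlabelled, and the synopsis and sections 1.2.1 and 3.1 supply the assignment.
- **That up to 30 of the 60 eyes escape all eye-level criteria**, because section 4.1.1 says a patient's "study eye must meet the following criteria to be eligible for inclusion in the study". The exclusions in section 4.1.2 apply to the patient, including ocular infection and altered nasolacrimal flow. Of the five inclusion items, only signs and symptoms of dry eye could be read per eye. The undefined term is loose wording, but that figure does not follow from it.
- **That the pregnancy test is missing from Visit 1.** Section 4.1.2 already requires it, and the check falls under the Visit 1 inclusion/exclusion item.

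**Conclusion.** The contradiction is real and direct. Section 5.1.1 gives 10 insert-treated eyes where section 1.2.1 states 20 and the SAP analyses 20. Because it is the only visit-level instruction on laterality, it is more than a background slip. The missing group labels in 5.1.1 and Table 1 are a genuine but lesser defect, since other sections resolve them.

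The effect on the results is conditional. The per-eye insert effect would be diluted by up to half only if one eye per patient was treated, both eyes were analysed, and the fellow eye had no insert effect. A reader might infer that this happened; the documents do not show it, and the SAP reports the opposite. This review takes no position on which instruction is clinically right, only that the passages disagree and must be reconciled.

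**What to change.** 1. Reconcile section 5.1.1 with the synopsis, sections 1.2, 1.2.1 and 3.1 and the SAP, so that all give the same number of treated eyes per patient.
2. List the Visit 1 treatments by group in section 5.1.1 and in Table 1.
3. From the accountability records required by section 4.2.3, confirm how many eyes of each study-group patient received an insert, and state that count in the SAP beside the 20 analysed eyes. The insert visualization scheduled at each visit can serve as a cross-check if it was recorded by eye.
4. If any analysed insert eye had no insert, report the number and show the insert-group results by treatment actually received.

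The cost is wording changes and a review of the records for 10 patients. No new patients, visits or measurements are needed. Because the results are already reported, item 3 is the part that still bears on their interpretation.
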